#### Randomisation

Randomisation across the full study (internal pilot + efficacy)

Randomisation is **at the unit of teams of practitioners**. The rationale for this is that practitioners within the same team interact a lot with each other. Randomisation at the level of the practitioner would therefore create too much of a risk of cross-contamination.

Randomisation is **stratified at the LA level**. This model ensures that there will be trained and control teams in all participating LAs, a configuration that aligns well with the model of funding for delivery of the intervention.

Randomisation happened in three phases, that correspond to three batches of funding for programme delivery mentioned earlier: the Home Office phase (December 2021), the pilot phase (spring 2022) and the efficacy phase (summer 2023). The randomisation procedure was the same at all phases, to ensure continuity and in line with the internal nature of the pilot. Specifically, in an initial step LA put forward a list of so far untrained teams that they have available for delivering Your Choice. Among LAs that have two or more teams available for training, the evaluators randomly select teams for being trained and teams for being controls. The randomisation code is developed in STATA 16. The outcome of the randomisation is communicated to LAs by the evaluators, and the training of selected teams is implemented.

To check adherence to randomisation in the efficacy trial, we will require LAs to provide a list of practitioners in each of the teams involved in the study and to let us know if and when they have been trained ahead of start of delivery in the efficacy phase.

Practitioners will know whether they are part of a treated or control team and therefore cannot be blind to the experimental assignment. When recruiting young people, practitioners will know the young person's experimental condition. This means that the young person may not be blind to the assignment at the time of recruitment. Training of practitioners and SPOCs around recruitment will strongly emphasize the need to recruit young people into the study (as opposed to an experimental arm) and to not divulge their treatment condition.

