#### Introduction

The Your Choice programme is a Cognitive Behavioural Therapy (CBT) enhanced approach to practice, delivered through high intensity contact within adolescent services to young people aged 11-18 at medium to high risk of contextual harm. The 12-18-week programme is delivered by specially trained practitioners, who are trained in CBT tools and techniques and are supported by regular clinical supervision. Training for practitioners is delivered through a train the trainer model by clinicians with experience in the delivery of CBT.

The impact evaluation is based on a two-armed cluster randomised controlled trial (RCT) where the unit of randomisation is teams of youth practitioners. Teams supporting young people eligible for Your Choice are randomly assigned to train in and deliver Your Choice (treatment group) or to supporting young people following Business As Usual (BAU) practices (control group). Teams randomised out of training during the efficacy trial will be offered to be trained in Your Choice later on.

Randomisation is done within all participating Local Authorities (LA) of London. The trial therefore involves a small unit of randomisation (teams) within small strata (all but two LAs have 10 or fewer than 10 teams), with an expected number of observations over 10 young people recruited in team on average. De Chaisemartin and Ramirez-Cueller (2024) show that, in such a case, the regular practice of clustering standard errors at the unit of randomisation can lead to downward bias in estimates of the variance of the treatment effect, resulting in over-rejecting the null hypothesis (of no effect). They advise that standard errors should be clustered at the strata level (LA) when RCTs have this type of configuration (and this result holds whether or not strata fixed effects are controlled for). To accommodate for these results, we perform power calculations via simulations (instead of using traditional power calculations commands).

<sup>2 This was explicitly agreed with LAs given the reservations they had about randomisation. It seems unlikely that control teams react to the possibility of future training so much in advance. LAs also have an obligation towards the young people they see, to deliver statutory services according to the BAU processes. For these reasons, this setting is unlikely to affect results.

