suggested in McConnell and Vera-Hernandez (2015). The simulation code used to perform these calculations is enclosed but we describe the steps used to perform these simulations below.

Each simulation is characterised by five parameters:

- Standard deviation of the outcome (σ)
- Intra-cluster correlation (ρ)
- Minimum Detectable Effect (β)
- Attrition rate (r)
- A threshold on the continuous outcome above which the binary indicator takes the value 1 and 0 otherwise (η)

Each simulation is based the following steps:

- 1. Randomise teams to be newly randomised to treated or control within each LA with 50-50 split.
- In LAs that have an odd number of teams to randomise, we randomly select whether (n+1)/2 or (n-1)/2 teams would get treated (where n is the number of teams to randomise)
- 3. Generate a normally distributed random variable at the Local Authority level,  $\theta_j$ , of mean 0 and variance  $\rho\sigma^2$
- 4. Generate a normally distributed random variable at the young person level,  $\epsilon_{ij}$ , of mean 0 and variance  $(1 \rho_{-})\sigma^2$
- 5. Implement the following data generation process for the outcome Y:

$$Y_{ij} = \beta T_{ij} + \theta_j + \epsilon_{ij}$$

where  $T_{ij} = 1$  if participant *i* is recruited in a treated team and 0 in a control team

- 6. Create a binary outcome  $D_{ij}$  such that it takes the value 1 if the score above is above a particular threshold  $\eta^9$  and 0 otherwise
- 7. Estimate OLS regressions of the chosen outcome (continuous  $Y_{ij}$  or binary  $D_{ij}$ ) on the treatment dummy, clustering the standard errors at the LA level, with or without controlling for Local Authority fixed effects, on a randomly selected sample of observations of size (1-*r*) of the expected number of study participants in order to

<sup>9 This threshold is chosen such that the mean of D is equal to the probability of observing our primary outcome in the baseline pilot data.

<sup>10 This step is to report power calculations for the binary outcome based on the continuous score, though the data generating process assumed here only enables us to simulate average impacts on the continuous score and hence may miss possibly stronger impacts the intervention may have at the top of the distribution

simulate a random attrition rate *r* to which we add the 83 observations from pilot that have endline data.

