#### Table 5: Structure of the two datasets used to perform power calculations

Although randomisation during the efficacy phase allocates teams to training and control on a 50-50 basis, legacy randomisation from the Home Office and pilot phases means more teams are trained than control. The power calculations reported above account for this imbalance.

Our power calculations account for a 30% attrition rate. This attrition rate is calculated based on all participants ever recruited in randomised teams in the pilot and efficacy trials (regardless of not they collected any endline data).

Table 6 report the MDE estimated using the simulation methodology described above, under the below assumptions about power, significance level and the type of test we want to perform and under different assumptions about the attrition rate and about whether Local Authority fixed effects are controlled for in the regression. Note that, when we revised the expected sample size in January 2025, we also revised our assumptions about the ICC and mean of the baseline based on estimates of these parameters in the baseline sample recruited during efficacy, which we deemed more reliable than the pilot sample due to its much greater size.

These assumptions turned out to be less conservative than those made when we initially ran power calculations: the ICC was lower (0.09 as opposed to 0.12) and the mean of the primary outcome variable was higher (0.6 as opposed to 0.3). This meant that, even though the revised sample size in scenario 2 is lower than the initial sample size in scenario 1 the MDE is slightly lower (22% instead of 24%).

Table 6: Minimum Detectable Effect on primary outcome (binary indicator for high to very high range of conduct problems) under the assumption we do not control for lagged outcome in the larger dataset

Scenario	Scenario 1: Sample A with original priors for simulation parameters (1.0 original version)	Scenario 2: Sample B with revised priors for simulation parameters (1.1 January 2025 update)
Alpha 	0.05	0.05
Power	0.8	0.8

<sup>11 Please adjust as necessary for trials with multiple primary outcomes, 3-arm trials, etc., when a Bonferroni correction is used to account for family-wise errors.

One-sided or two-sided?	Two-sided	Two-sided
ІСС	0.12	0.09
Mean of the primary outcome in control group	0.3	0.6

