#### Intra-cluster correlations (ICCs)

Clusters are teams of practitioners but given the discussion above about power, we will cluster standard errors at the LA level. We will calculate ICCs for both team and LA using the `estat icc' command in Stata.

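### The power simulation gives all intra-cluster variance to the Local Authority and none to the randomised teams: the original 24% MDE is too favourable if the ICC is partly at team level, and the current 22% does not reproduce

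*SAP*

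**What the plan says.** The SAP Introduction states that "the unit of randomisation is teams of youth practitioners", stratified by LA. The section on intra-cluster correlations says "Clusters are teams of practitioners but given the discussion above about power, we will cluster standard errors at the LA level". The Protocol (Randomisation) explains why teams are randomised: "practitioners within the same team interact a lot with each other".

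The simulation has two random terms. Step 3 is "Generate a normally distributed random variable at the Local Authority level", with variance ρσ². Step 4 is "Generate a normally distributed random variable at the young person level", with variance (1−ρ)σ². Step 5 adds these to the treatment effect, and no term is indexed by team. Step 7 fits OLS with LA-clustered standard errors, "with or without controlling for Local Authority fixed effects". The Protocol (Sample size calculations) has the same steps.

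SAP Table 6 gives an MDE of 24% for Scenario 1 (ICC 0.12, mean 0.3) and 22% for Scenario 2 (ICC 0.09, mean 0.6, the January 2025 update). The text before the table credits the smaller Scenario 2 MDE to the lower ICC and the higher mean together. The SAP discussion of MDEs translates 22% at a mean of 0.6 into 10.8 percentage points.

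**The concern.** Treatment varies between teams inside each LA. The sampling variance of the treatment contrast therefore depends on how much teams within an LA differ, and the simulation sets that to zero. An effect shared by every team in an LA is absorbed by LA fixed effects, which the primary model includes (SAP, Primary outcome analysis). The stated ICC then enters only by shrinking the residual variance to (1−ρ)σ².

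At stake is the sensitivity claimed for the trial. The MDE supports the argument that plausible effects are detectable. If it is too small, a null result may be read as ruling out effects that the trial had little chance of finding.

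**Working it through.** **Inputs from the documents.**
- Scenario 1: 1,857 recruited in 138 teams, 30% attrition, so 0.7 × 1,857 ≈ 1,300 analysed (0.7 × 960 = 672 intervention, 0.7 × 897 ≈ 628 control); 9.4 analysed per team (SAP footnote); ρ = 0.12; mean 0.3.
- Scenario 2: 1,563 recruited in 132 teams (83 intervention, 49 control), 1,094 analysed, split 937:626 into 656 and 438; 1,094/132 = 8.3 per team; ρ = 0.09; mean 0.6.
- Both: two-sided 5%, 80% power, 29 LAs, median 3 teams per LA, largest 21 and 12.

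**Assumptions, because the documents do not give them.** The exact number of teams per LA (built to match the figures above), the coefficient of variation (CV) of team size (0.5, varied from 0 to 1), and the level at which ρ was estimated.

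**Step 1: the Protocol's continuous MDE.** Analysed n = 0.7 × 1,678 + 83 ≈ 1,258. With no clustering at all, MDE ≈ 2.8 × 2/√1,258 = 0.158 SD. Protocol Table 6 states 0.16 with fixed effects at ICC 0.12, so the ICC cost nothing. With a team-level design effect of 1 + (9.4 − 1) × 0.12 = 2.01, the MDE is 0.158 × √2.01 ≈ 0.22 SD. Simulating the described steps gives 0.155-0.163 with fixed effects and 0.174-0.193 without (stated 0.16 and 0.17). Moving the ICC to teams gives 0.24-0.27.

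**Step 2: binary MDE by formula.** Solve δ = 2.80 × √{D[p₀(1−p₀)/n₀ + p₁(1−p₁)/n₁]} with p₁ = p₀ − δ and D the design effect.
- Scenario 1: D = 1 gives δ = 0.0686 (22.9% of 0.3); D = 2.01 gives 0.0953 (31.8%).
- Scenario 2: D = 1 gives 0.0854 (14.2% of 0.6); D = 1 + (8.29 − 1) × 0.09 = 1.66 gives 0.110 (18.3%).

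**Step 3: binary MDE by simulating steps 1-7** (team-size CV 0.5; with / without LA fixed effects).

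| Where ρ is placed | Scenario 1 (stated 24%) | Scenario 2 (stated 22%) |
|---|---|---|
| No clustering | 24.9% / 23.8% | 16.0% / 15.1% |
| All at LA, as described | 23.7% / 25.7% | 15.8% / 16.9% |
| Half LA, half team | 28.6% / 28.9% | 17.2% / 17.4% |
| All at team | 32.0% / 30.7% | 19.3% / 18.6% |

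Scenario 1 reproduces. A second set-up (134 teams, 1,258 analysed, CV up to 0.6) gives 24% / 25% at LA level, 28-30% for the even split and 31-33% at team level. Over CV 0 to 1, the Scenario 1 team-level MDE runs from 30% to 35%.

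Scenario 2 does not reproduce. Other choices of fixed effects and CV raise the LA-level result to at most 18.7%, and reading ρ on the binary scale raises it to about 20%. A mean of 0.4 with fixed effects gives about 23%, but nothing in the SAP shows that this was used.

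**Step 4: power at the stated effects, all of ρ at team level.**
- Scenario 1 at 24%: 56-59% (54-59% across both set-ups), against about 82% as described with fixed effects. The even split gives 63-70%.
- Scenario 2 at 22%: 87-92%. At 10.8 points: 73-79%.

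**Step 5: the printed Scenario 2 figures.** 0.22 × 0.6 = 13.2 points, whereas 10.8/60 = 18%.

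**Step 6: the role of the lower ICC.** With fixed effects the continuous MDE scales with √(1−ρ). Going from 0.12 to 0.09 multiplies it by √(0.91/0.88) = 1.017, a slight increase. Without fixed effects an LA-level ICC does cost something (Scenario 1: 25.7% against 23.8% with none), so lowering it helps a little.

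**The case against.** Several objections carry weight.

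- **LA clustering of standard errors follows the cited small-strata result.** This stands for inference: LA-clustered errors allow for correlation within and between teams in an LA, so the planned test is not impugned. It does not rescue the simulation, because the standard error can only reflect variance that was generated.
- **The ICCs may have been estimated at LA level.** The documents do not say. If they were, the within-LA team component is unknown and could be small. A team term would still be needed, but 31-33% would be the wrong size.
- **The primary model adjusts for the baseline outcome.** Protocol Table 4 gives a residual ICC of 0.05. With that at team level, the Scenario 1 MDE is roughly 28% and power at 24% about 68%. This softens the loss, but Protocol Table 7, which mimics that adjustment, still states 24-25%.
- **Scenario 1 has been superseded.** It has, on inputs that the SAP considers more reliable. A reader might infer that the January 2025 extension rested on an overstated power claim. The numbers do not support this: with 0.09 at team level the MDE is below 22%. It passes 22%, reaching about 24%, only if ρ is read on the binary scale and team sizes are very uneven (CV 1).
- **The results will carry confidence intervals, and both team and LA ICCs will be reported.** This limits the harm to how the planning figures are read.

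**Conclusion.** The simulation omits the variance between the units that are randomised. For Scenario 1 and Protocol Tables 6 and 7, the stated MDE is too favourable to the extent that the ICC lies between teams. The sizes given for all or half of 0.12 at team level rest on an assumed split, on reconstructed team and LA sizes, and on no baseline adjustment, as in SAP Table 6.

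For Scenario 2 the finding is different: 22% follows neither from the SAP's own steps nor from its own percentage-point figure. Whether the current claim is optimistic depends on which figure is meant. Against 13.2 points, power remains above 80% with the ICC at team level; against 10.8 points it falls slightly short.

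Two stronger readings should be resisted. The planned estimator and standard errors are not shown to be invalid. Nor is the SAP's remark about the lower ICC simply backwards: it fails with LA fixed effects and holds weakly without them, and SAP Table 6 does not say which specification it reports.

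**What to change.** 1. State the level (team or LA) and the scale (continuous or binary) at which 0.12 and 0.09 were estimated.
2. Add a team-level random effect at step 3, keeping the LA effect, and estimate both variance components from the baseline data already held.
3. Rerun SAP Table 6 and Protocol Tables 6 and 7 with the actual numbers of teams per LA and young people per team. Replace the 24% and 22% figures, in the tables and in the discussion of MDEs, with the results.
4. Reconcile 22% with 10.8 percentage points.
5. Say whether SAP Table 6 uses LA fixed effects, and revise the sentence crediting the lower ICC, since with fixed effects a lower LA-level ICC does not reduce the MDE.

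The cost is minor recoding, revised text and possibly a less favourable stated MDE. Enrolment and the primary analysis are unchanged.

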#### Table 4: Values picked for parameters in simulations and justification

	Scenario 1 (original assumptions held at the beginning of the trial)	Scenario 2 (assumptions updated as part of the January 2025 revision)
Attrition Rate	30%	30%
Mean of primary outcome	0.3 (estimated on relevant baseline and endline pilot data)	0.6 (estimated on baseline efficacy and pilot data available at the time of revision)
Intra-cluster correlation (ρ)	0.12 (estimated on relevant baseline and endline pilot data)	0.09 (estimated on baseline efficacy and pilot data available at the time of revision)
Minimum Detectable Effect	A grid of values between 10% and 40% reduction in the primary outcome (likelihood to have high/very high SDQ conduct problem score) (This is obtained by simulating the continuous outcome with SD $\sigma$ = 1 and using a grid of MDES 6 on the continuous SDQ score appropriate so that the MDES on the binary primary outcome varies between 10% and 40% of the primary outcome mean).	

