	Attrition rate = 30%	No strata fixed effects	MDE = 0.17
Continuous score of externalising difficulties (standardised to have SD 1)		Strata fixed effects	MDE =0.16
	Attrition rate = 40%	No strata fixed effects	MDE =0.18
		Strata fixed effects	MDE =0.17
Binary score for scoring in high or very high range on conduct problems (probability of outcome in control group assumed to be 25%)	Attrition rate = 30%	No strata fixed effects	MDE = 24% of control mean
		Strata fixed effects	MDE = 23% of control mean
	Attrition rate = 40%	No strata fixed effects	MDE = 25% of control mean
		Strata fixed effects	MDE = 25% of control mean

-

<sup>13 Please adjust as necessary for trials with multiple primary outcomes, 3-arm trials, etc., when a Bonferroni correction is used to account for family-wise errors.

Table 7: Minimum Detectable Effect under the assumption we do control for lagged outcome that reduces the variance of the underlying outcome to 0.6 and the ICC to 0.05

21 1 14	0.05		
Alpha 	0.05		
Power	0.8		
One-sided or two-sided?	Two-sided		
ICC	0.05		
Variance of continuous score	0.6		
	Attrition rate = 30%	No strata fixed effects	MDE = 0.12
Continuous score of externalising difficulties		Strata fixed effects	MDE = 0.12
(standardised to have SD 1)	Attrition rate = 40%	No strata fixed effects	MDE = 0.13
		Strata fixed effects	MDE = 0.13
Binary score for scoring in high or very high range of the conduct problem scale	Attrition rate = 30%	No strata fixed effects	MDE = 24% of control mean
		Strata fixed effects	MDE = 24% of control mean
	Attrition rate = 40%	No strata fixed effects	MDE = 25 % of control mean
		Strata fixed effects	MDE = 25% of control mean

-

<sup>14 Please adjust as necessary for trials with multiple primary outcomes, 3-arm trials, etc., when a Bonferroni correction is used to account for family-wise errors.

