Number of participants	Due to lower-than-expected recruitment and higher than expected attrition, in January 2025 the recruitment period was extended to the end of February 2025. To inform this decision, we re-estimated the number of participants based on recruitment to date and new information from the Local Authorities and revised the number of participants down to 1,563 young people recruited across the internal pilot and efficacy trial recruited between August 2023 and end of February 2025. Across teams that have ever been randomised, this included an expected 1,402 young people recruited between August 2023 and February 2025 and 161 young people who were recruited during the internal pilot phase (82 of whom we have endline data for). We expect a 70% data completion rate across the internal pilot and efficacy trials, which sets the overall sample for impact evaluation at 1,094.		
Primary outcome and data source	Indicator for scoring in the high or very high range of the conduct problems subscale of the Strengths and Difficulties Questionnaires (SDQ). The high and very high range threshold is defined by the SDQ's four-fold categorisation.		
	The SDQ is taken at the start and end of the young person's pathway through the programme, at weeks 1 and 20 after		

	recruitment. In both cases, they are administered during a session with the practitioner, as part of the baseline and endline surveys. Some small variation in the timing of these surveys is allowed, to accommodate differing start and end dates for the programme and convenience in scheduling meetings between participants and practitioners. Below we will be referring to week 1 and 20 as expected times for these surveys.
	Criminal activity : Indicator for recorded arrest in Police National Computers during first 16 months after recruitment (allowing for 4-months treatment plus 1 year following treatment).
	Self-reported and practitioner-reported perceptions of young person's safety: Young person and practitioner versions of "Checkpoint. A safety scale for young people", which is an instrument to measure young people's perceptions of safety developed by the research team. Measured at baseline and endline as part of the participant's and practitioner's surveys (weeks 1 and 20 after recruitment, respectively).

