8. Repeat steps 1 through 6 1000 times and compute the power as the proportion of times the coefficient  $\beta$  is significant at the 95% level.

As part of this exercise, we wanted to explore the power implications of controlling for a lagged (baseline) outcome. Instead of making additional assumptions to simulate such baseline outcome, we instead performed the simulation above with smaller values of the variance of the outcome variable and of the ICC in order to mimic the effect of controlling for a lagged outcome on these parameters as estimated using data from the pilot period.

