#### Discussion of MDEs in the context of the pilot trial and of the literature

The power calculations in Table 6 above indicate that, under a 30% attrition rate and based on the best information we have at the beginning of the trial about key parameters (Scenario 1), we could detect with 80% power a minimum effect of 24% of baseline probability to be in the high to very high range of conduct problems in the sample expected based on information provided by Local Authorities before the start of the trial (whereby 138 teams recruit 1857 young people). Of a 0.3 mean probability to be in the high to very high range of conduct problems, this would be equivalent to a reduction of 0.072 percentage points.

Revised power calculations based on the updated values for the simulation parameters as of January 2025 (Scenario 2) indicate that we could detect with 80% power a minimum effect of 22% of baseline probability to be in the high to very high range of conduct problems. For a 0.6 mean probability to be in the high to very high range of conduct problems, this would be equivalent to a reduction of 10.8 percentage points.

Under both Scenario 1 and Scenario 2, the MDE is within the range of impacts suggested by the endline data, well below the effects of CBT interventions on externalising behaviours, such as Attention Deficit Hyperactivity Disorder, Conduct Disorder and Oppositional Defiant Disorder, which are reported in the literature and which range around 60-70% (Gaffney, Farrington and White, 2021). Given that Your Choice is implemented on a large scale and delivered by non-clinical practitioners, it would be reasonable to expect a lower impact than

<sup>12 Gaffney, H., Farrington, D. and White, H. (2021). "Cognitive Behavioural Therapy: YEF Toolkit technical report"

the impact of CBT interventions reported in most of the literature. Yet, an effect size of 22% or 24% reduction (or a third or the impact sizes reported in the literature) still seem within the range of reasonable effects to expect from the Your Choice intervention.

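### Scenario 2 uses a baseline prevalence as the week-20 control mean and keeps 30% attrition; its 22% MDE and 1,094 analysed are not supported, and the 22% does not follow from its own inputs

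*SAP*

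**What the plan says.** The primary outcome is the week-20 indicator for a high or very high SDQ conduct problems score (SAP, Design overview).

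**Mean.** For Scenario 2, SAP Table 4 gives the mean as "0.6 (estimated on baseline efficacy and pilot data available at the time of revision". Table 6 carries the same 0.6 in a row headed "Mean of the primary outcome in control group". Scenario 1 used 0.3, from baseline and endline pilot data. The text under Table 5 credits the lower ICC and the higher mean for the relative MDE falling while the sample shrank.

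**Attrition.** The participants row of the SAP's summary table opens the account of the extension with "Due to lower-than-expected recruitment and higher than expected attrition". It then says: "We expect a 70% data completion rate across the internal pilot and efficacy trials, which sets the overall sample for impact evaluation at 1,094". The text under Table 5 states: "Our power calculations account for a 30% attrition rate". That is the rate assumed at the start. No observed efficacy completion rate is given.

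**Result.** For Scenario 2 the SAP's discussion of MDEs says "we could detect with 80% power a minimum effect of 22% of baseline probability", and equates this to 10.8 percentage points on a mean of 0.6.

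**The concern.** Two planning inputs do not match what they stand for. A prevalence measured at week 1 is used as the control-arm rate at week 20, and no endline figure is offered in support. The attrition rate is unchanged in a revision that was prompted partly by attrition above that rate.

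The resulting 22% and 1,094 are what the SAP uses to argue that the extended trial is still adequately powered, and they will frame how a null result is read. A relative MDE is sensitive to the mean in its denominator, so an unsupported mean makes the headline figure unreliable in either direction. The protocol showed results at both 30% and 40% attrition. For Scenario 2 the SAP shows only one value, although the text introducing Table 6 speaks of several.

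**Working it through.** **1. Analysed sample.**
- Stated figure: 0.70 × 1,563 = 1,094.1, so 1,094 reproduces.
- Pilot completion is already known: 82/161 = 50.9%.
- Implied efficacy completion: (1,094 − 82)/1,402 = 1,012/1,402 = 72.2%.
- The original total was built differently: 0.70 × 1,698 + 83 = 1,271.6, the stated 1,272. The same rule now gives 0.70 × 1,402 + 82 = 1,063.
- At 60% efficacy completion: 0.60 × 1,402 + 82 = 923. At 50%: 0.50 × 1,402 + 82 = 783.
- Approximate inflation of the MDE relative to 1,094: √(1,094/1,063) = 1.01, √(1,094/923) = 1.09, √(1,094/783) = 1.18.

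The SAP is also not uniform on this. Its simulation step 7 adds the pilot completers (83 there, 82 elsewhere) to the retained share, while the text under Table 5 applies 30% to everyone recruited in randomised teams.

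**2. The two forms of the stated MDE.** 0.22 × 0.6 = 0.132, or 13.2 percentage points. The stated 10.8 points is 10.8/60 = 18% of 0.6.

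**3. Closed-form check, no clustering.** Sample B at 70% gives 0.7 × 937 = 656 intervention and 0.7 × 626 = 438 control. For two-sided 5% and 80% power, the MDE is 2.80 × √[p0(1−p0)/438 + p1(1−p1)/656].
- p0 = 0.6: 2.80 × 0.0305 = 0.085, which is 14% of 0.6.
- p0 = 0.3: 2.80 × 0.0273 = 0.076, which is 25% of 0.3.

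**4. The SAP's described simulation.** A latent normal score with a Local Authority (LA) random effect is dichotomised at a threshold, then analysed by OLS with LA-clustered standard errors. The layout of teams within LAs is assumed (29 LAs, median 3 teams, the largest 12 and 21, uneven team sizes), with 600 runs per point.
- Scenario 1 (mean 0.3, ICC 0.12, 0.7 × 1,857 = 1,300 analysed): 24.5% with LA fixed effects and 25.7% without. The SAP states 24%, so the method reproduces it.
- Scenario 2 (mean 0.6, ICC 0.09, 1,094 analysed): 15.4% with LA fixed effects and 17.2% without. The SAP states 22%, which is not reproduced.

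Relative MDE by endline control mean (LA fixed effects, ICC 0.09, overall attrition applied to 1,563):

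| Attrition (N) | 0.6 | 0.5 | 0.4 | 0.3 |
|---|---|---|---|---|
| 30% (1,094) | 15.3% | 19.0% | 22.9% | 28.3% |
| 40% (938) | 17.1% | 20.8% | 25.0% | 29.8% |
| 50% (782) | 18.6% | 22.4% | 27.2% | 32.0% |

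Allowing for simulation error, specification and the assumed layout, the first row is roughly 15-17%, 19-20%, 21-24% and 28-29%.

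In percentage points the first row is 0.153 × 60 = 9.2, 0.190 × 50 = 9.5, 0.229 × 40 = 9.2 and 0.283 × 30 = 8.5. The absolute MDE moves much less than the relative one.

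**The case against.** Several points on the other side stand.

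- **Disclosure.** The SAP says openly that the revised mean comes from the baseline sample, chosen for its size, and calls the new assumptions less conservative. That explains the source. It does not make 0.6 a control-group endline rate, which is how Table 6 labels it.
- **Direction.** A reader might infer that both inputs flatter the design and that correcting them must push the MDE above 22%. The documents do not support that. On the SAP's inputs the method gives 15-17%, so 22% is cautious if the endline mean really is 0.6. A mean of 0.5 with 40% attrition gives about 21%. At 30% attrition the figure passes 22% only when the endline mean is near or below 0.4.
- **An endline mean of 0.3.** A reader might take 0.3 as the true value. The SAP's 0.3 is partly baseline pilot data, and nothing shows prevalence halving by week 20. Nor is the protocol's 25% a pilot control result; its Table 6 gives it as "probability of outcome in control group assumed to be 25"%.
- **Scale.** Protocol Analysis step 3 scales effects to the baseline frequency. On a fixed denominator of 0.6, the 8.5 to 9.5 points above are 14-16%, which is still not 22%. The SAP's section on presentation of outcomes uses risk ratios, for which the endline control rate is what matters.
- **Attrition.** The text under Table 5 could mean that 30% is the observed pooled rate. That sits badly with attrition above expectation when 30% was the expectation, and no count is given. Fixing the pilot at 82 costs only about 1% in the MDE; the 60% and 50% cases are illustrations.
- **Data in hand.** That a year of endline forms existed by January 2025 is an inference from a planned timeline, and the pilot reported patchy, late endline returns.

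**Conclusion.** The concern holds as a failure of support and of internal consistency. It does not show that the trial is underpowered. The 0.6 is a baseline prevalence in the place of a week-20 control mean. The 1,094 needs 72.2% efficacy completion, better than the 70% first planned, in a revision prompted partly by worse attrition. The 22% neither follows from its stated inputs nor agrees with 10.8 points.

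With 1,094 analysed, the relative MDE runs from about 15% to 29% as the endline control mean goes from 0.6 to 0.3, and is about 1 to 2 points higher at 40% attrition. The documents give neither the endline mean nor the observed efficacy completion, and the layout of teams within LAs is assumed, so these are ranges. The arithmetic on N and on 13.2 against 10.8 points needs no such assumption.

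This should be fixed, but it does not affect the validity of the analysis: no estimand, estimator, test or final confidence interval changes, and the extension has already been decided.

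**What to change.** - Label 0.6 in SAP Tables 4 and 6 as baseline prevalence.
- Set the control mean from the pooled, arm-blind endline prevalence if available; otherwise show a range, for example 0.3, 0.45 and 0.6.
- Set attrition from observed completion among efficacy recruits past week 20, or show 30%, 40% and 50%. State whether the 30% is observed or assumed.
- Compute N as 82 + completion × 1,402, and make simulation step 7 and the text under Table 5 agree with it.
- Rerun the simulation and restate the MDE in relative and percentage-point terms that agree, replacing 22%, 10.8 points and 1,094.

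The cost is two pooled figures if they are to hand, one rerun over a short grid and some SAP wording. The stated MDE may become less favourable. Trial conduct is unaffected.
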